### Loss of Confidentiality:

Any time information is collected, there is a potential risk for loss of confidentiality. Every effort will be made to keep the subject's information confidential; however, this cannot be guaranteed.

### Blood Draw Risk:

Each subject will have two blood draws collected throughout their participation in the study. Risks of taking a blood draw include pain, a bruise at the point where the blood is taken, redness and swelling of the vein, and infection. There is a rare risk of fainting. These blood draws are part of the standard of care and will not place study subjects at any additional risk.

### IV Placement Risk:

Each subject will receive IV Iron or placebo based of randomization group. Risks of IV placement are possible pain, bruising, and infection at the site of the needle stick where the IV is placed.

Anxiety (nervousness) may possibly be experienced during the placement of the IV.

## **10. Subject Safety and Data Monitoring:**

The PI and research coordinator will be responsible for monitoring the safety of this study, this will occur on a quarterly basis. The monitoring will include participant demographics, expected versus actual recruitment rates, summary of any quality assurance or regulatory issues, summary of adverse events (AEs) or serious adverse events (SAEs) which may have occurred. AEs and SAEs will be reported per IRB policies.

## **11. Procedures to Maintain Confidentiality:**

Data collection will be identified with a participant ID number. Data will be collected and stored with the participant ID code only. The master enrollment log linking subject identifiers with study ID numbers will be kept in a password-protected database. Relevant data variables (specified under outcomes) will be collected by chart review and placed into an Excel or Access file. These files will not contain identifiable information and will be stored in password protected, secured UTMB servers. The research coordinator and PI will be available to monitor the data and correct any discrepancies based on source documents if needed.

## **12. Potential Benefits:**

The potential benefits of the study to the intervention group (IV iron) include:

1. Improved fractional absorption of iron with corresponding improvement of anemia compared to standard oral iron replacement therapy
2. Decreased GI side effects with IV iron
3. Faster increase in hemoglobin

## **13. Biostatistics:**

We hypothesize that the IV iron group will have a higher hemoglobin level at 6 weeks postpartum compared with the oral group. The primary analysis will be conducted on an intention-to-treat basis. Between-group differences in continuous variables will be assessed using Student t test or Man-Whitney rank sum test and results will be given as mean, standard deviation or median range as appropriate. Categorical variables will be assessed using the Pearson chi-square test or Fisher exact test as appropriate. For dichotomous endpoints, relative risk (RR) and 95% CI values will be calculated. P <0.05 will be considered significant. The analysis will be performed after study completion.

Based on data from the literature, we estimate that women who received oral iron will have a mean 6 week postpartum hemoglobin of 11.2 g/dL with a standard deviation of 1.2. We anticipated that women that receive IV Iron will have a postpartum 6 weeks mean hemoglobin of 12.4 g/dL. Using calculated effect size, power of 80% and 2-sided alpha of 0.05, we estimate that we will need 38 (19/group) subjects with complete ascertainment. Accounting for 5% lost to follow up, the final sample size would be **40**.

We will be performing a superiority approach. Stata 16 will be used for the statistical analysis.

**t tests - Means:** Difference between two independent means (two groups)

**Analysis:** A priori: Compute required sample size

**Input:** Tail(s) = Two

Effect size d = 0.9592329

$\alpha$  err prob = 0.05

Power (1- $\beta$  err prob) = 0.8

Allocation ratio N2/N1 = 1

**Output:** Noncentrality parameter  $\delta$  = 2.9565544

Critical t	=	2.0280940
Df	=	36
Sample size group 1	=	19
Sample size group 2	=	19
Total sample size	=	38
Actual power	=	0.8203999

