
**Brief Study Design and Rationale**

Patients randomly assigned to 2 groups will be compared:

1. **Oral Iron group:** Ferrous sulfate 325 mg (65 mg elemental iron) by mouth for a total of 6 weeks TID.

1.1 IV placebo in sodium chloride 0.9% 500mL infusion will be given before discharge home over 1.5 hour, preceded by placebo test dose IV infusion of 100mL 0.9% sodium chloride.

2. **IV Iron group:** Low molecular weight iron dextran (infed) 1000mg in sodium chloride 0.9% 500mL IV infusion over 1.5 hour, preceded by test dose of 25 mg IV low molecular weight iron dextran infusion in 100mL 0.9% sodium chloride.  
2.1 Oral placebo will be given by mouth for a total of 6 weeks TID.

The standard of care at UTMB for the detection and treatment of postpartum iron deficiency anemia is as follows. All postpartum patients undergo blood draws at their first postpartum day for anemia screening. Those patients who are identified as anemic (hemoglobin < 12 g/dL) then receive oral iron supplementation. There are many different iron supplements that are used at UTMB to treat iron deficiency in pregnancy. These supplements vary in elemental iron content, enteral coatings, and supplements combined with vitamins and minerals. The choice of which iron supplement is left to the discretion of the provider caring for the patient. Among these choices, ferrous sulfate (325mg, with 65mg elemental iron) is very commonly prescribed to UTMB patients and thus is the oral iron therapy that will be used for this study. Standard UTMB treatment surveillance includes blood draws at the 3 and 6 weeks routine postpartum visits. This study will follow the UTMB standard treatment surveillance protocol and thus study participants will have no study specific blood collections.

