## Screening

All pregnant patients who deliver in our unit undergo a laboratory screen for anemia at the first postpartum day as part of the UTMB standard of care while recovering in the hospital. Eligible patients (PPD#1 patients with a hemoglobin less than 9 g/dl) will be screened and approached while inhouse (detailed under section 8).

The anticipated procedures flow is as follows

1. Research staff will go to postpartum ward.
2. Research staff will confirm with provider that possible subjects are appropriate candidates for treatment with ferrous sulfate.
3. Research staff will approach screened patients to obtain consent from possible subjects.
4. Subjects will be randomized using a computer-generated sequential randomization log with group assignment, subject name, and medical record number.
5. After patient is consented and enrolled, the provider will be notified orders will be placed in EPIC by providers with the assistance of the research staff; and a note will be placed in the electronic chart indicating that the patient is enrolled in the study.
6. Subjects will continue to receive standard, routine postpartum care and surveillance of postpartum iron anemia.
  - a. Research staff and PI will periodically monitor surveillance data by chart review.
7. During their routine 6 weeks postpartum visit, patient's hemoglobin level will be obtained (standard of care at UTMB). If subjects have a hemoglobin level drawn before the 6 weeks visits, such as in the 3 weeks postpartum visit, we will also collect this information.
8. Research staff will conduct chart review to obtain the data points for the primary and secondary outcomes (described in section 1)

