## Outcomes

Our primary outcome will be hemoglobin level at 6 weeks postpartum. Based on the available evidence we hypothesize that IV iron supplementation will be superior or at least not inferior to oral iron supplementation. Additionally, we aim to assess the secondary outcomes as listed in the introduction obtained by chart review. Data to be collected includes population characteristics including demographics and data points described in the outcomes listed under the introduction obtained by chart review.

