## **5. Criteria for Inclusion of Subjects:**

- Maternal age  $\geq$  18 years and  $<$  50 years
- Delivery at UTMB
- Hemoglobin below 9 g/dl in postpartum day 1: This population has the highest risk to have complications from postpartum anemia, protracted recovery and the most to benefit from IV iron (4 studies showed benefit of IV iron at 6 weeks PP in subjects with baseline hemoglobin values ranging from 7.4 to 8.1 g/dL.)
- Singleton gestation

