## **6. Criteria for Exclusion of Subjects:**

- Enrolled in another trial that may affect outcome at the discretion of the PI
- Diagnosis of malabsorptive disorder or history of gastric bypass procedure
- Known diagnosis of anemia other than iron deficiency (thalassemia, macrocytic anemia, sickle cell, etc.)
- Significant cardiovascular disease, including but not limited to myocardial infarction or unstable angina within 6 months prior to study inclusion or current history of NYHA Class III or IV congestive heart failure
- Patient has received blood transfusion or there is a plan to transfuse
- Lactose intolerance

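### The 6-week hemoglobin comparison leaves day 1 hemoglobin unused: adjusting for it would be a low-cost improvement with a small expected gain, not the correction of an error

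*Combined protocol and SAP*

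**What the plan says.** The Outcomes part of section 3 states: "Our primary outcome will be hemoglobin level at 6 weeks postpartum". For the analysis, section 13 states: "Between-group differences in continuous variables will be assessed using Student t test or Man-Whitney rank sum test". No covariate, ANCOVA, change-from-baseline or stratified analysis appears anywhere in the document.

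The sample size in section 13 rests on the same unadjusted comparison ("Using calculated effect size, power of 80% and 2-sided alpha of 0.05"). It gives 19 evaluable women per group and an actual power of 0.8204.

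The baseline value is available. The Brief Study Design and Rationale says: "All postpartum patients undergo blood draws at their first postpartum day for anemia screening". The Screening part of section 3 repeats this, and section 5 makes the result an entry criterion: "Hemoglobin below 9 g/dl in postpartum day 1". Screening describes the allocation as a "computer-generated sequential randomization log with group assignment", with no mention of stratification. As described, neither the randomization nor the analysis uses the baseline value of the primary outcome.

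**The concern.** A baseline measurement of the outcome variable is often the most useful covariate a small trial has. Here it costs nothing to collect and is complete by construction, because nobody can enter without it. Leaving it out has two possible consequences:

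- **Precision.** If day 1 hemoglobin predicts 6-week hemoglobin among eligible women, the unadjusted interval is wider than it needs to be.
- **Chance imbalance.** With about 19 women per arm and no stratification described, the arms can differ at baseline by luck. The unadjusted estimate carries part of that difference, and an adjustment chosen after seeing it would be post hoc.

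The validity of the trial is not at stake, and the feasibility decision does not depend on this point.

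**Working it through.** **Inputs from section 13.** Difference 12.4 - 11.2 = 1.2 g/dL; printed effect size d = 0.9592329; two-sided alpha 0.05; n = 19 per group. The printed d implies a common SD of 1.2/0.9592329 = 1.251 g/dL.

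**Reproducing the plan.** Noncentrality = d × √(n/2) = 0.9592329 × √9.5 = 2.9566; df = 36; critical t = 2.0281. Power is 0.8204, as printed (18 per group gives 0.798). The 95% CI half-width is 2.0281 × 1.251 × √(2/19) = 0.823 g/dL.

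**ANCOVA with one baseline covariate.** df = 35 and Var(difference) = SD² × (1 - ρ²) × (2/19) × (1 + 1/34). The last factor is the average cost of chance baseline imbalance. Here ρ is the within-arm correlation of day 1 with 6-week hemoglobin *among eligible women*.

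| ρ | Power | Half-width (g/dL) |
|---|---|---|
| unadjusted | 0.820 | 0.823 |
| 0 | 0.809 | 0.836 |
| 0.12 | 0.814 | 0.830 |
| 0.20 | 0.824 | 0.819 |
| 0.27 | 0.837 | 0.805 |
| 0.35 | 0.856 | 0.783 |
| 0.42 | 0.877 | 0.759 |

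Power equals the unadjusted value at ρ = 0.174.

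**What ρ is plausible?** The documents give no correlation and no day 1 distribution, so both are assumed. Take day 1 hemoglobin in all delivered women as normal with mean 10 to 11 and SD 1.3, cut off above at 9 g/dL. Let u be the ratio of the SD after the cut to the SD before it. An unselected correlation r then becomes r × u / √(1 - r² + r²u²). For means of 10, 10.5 and 11, u = 0.478, 0.427 and 0.383. Example: r = 0.5 and u = 0.427 give 0.2135/√(0.75 + 0.25 × 0.182) = 0.239.

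| Unselected r | ρ among eligible women | ANCOVA power |
|---|---|---|
| 0.3 | 0.12 to 0.15 | 0.814 to 0.817 |
| 0.5 | 0.22 to 0.27 | 0.827 to 0.836 |
| 0.7 | 0.35 to 0.42 | 0.857 to 0.879 |

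Powers in this table use unrounded correlations.

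**Wider assumptions.** Section 6 also excludes a woman if: "Patient has received blood transfusion or there is a plan to transfuse". That may trim the range from below. I varied the SD over 1.0, 1.3 and 1.6 and the mean over 10, 10.5 and 11, with no lower bound or one of 6.5, 7 or 7.5 g/dL: 3 × 3 × 4 = 36 settings. ρ becomes 0.08-0.16, 0.14-0.28 and 0.24-0.44 for r = 0.3, 0.5 and 0.7. Overall power runs from 0.811 to 0.884.

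**Simulation check.** With the truncated baseline (mean 10.5, SD 1.3; 100,000 trials per setting) and r = 0, 0.3, 0.5 and 0.7, ANCOVA power was 0.809, 0.815, 0.833 and 0.867. Unadjusted power was 0.818 to 0.822. Type I error was 0.050 to 0.051 for both tests.

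**Chance imbalance.** P(baseline means differ by at least 0.5 SD) = 2 × (1 - Φ(0.5/√(2/19))) = 2 × (1 - Φ(1.541)) = 0.123. A gap of exactly 0.5 SD shifts the unadjusted difference by 0.5 × ρ × 1.251: 0.075 g/dL at ρ = 0.12 and 0.263 g/dL at ρ = 0.42. Larger gaps shift it in proportion.

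**The case against.** The plan is internally consistent: a t test paired with a t-test sample size, in a trial whose stated purpose is feasibility. Chance imbalance is not bias, and the unadjusted test's error rate and interval already allow for it. The shifts above lie well inside the 0.82 g/dL half-width. All of this stands.

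The benefit also rests on assumed values, and over part of the range it is absent. Of the 36 settings, ρ falls below break-even in all 36 at an unselected correlation of 0.3, in 27 at 0.4 and in 5 at 0.5. Only 0.7 gives a consistent gain. This stands too: the documents cannot show that the effect on power is positive. The loss, however, never exceeds about 1 point, while the possible gain is several times that.

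Two objections concern the fix. Making the Mann-Whitney test secondary goes beyond adding a covariate, but it follows from naming a single primary model. The change covers hemoglobin only, although the Primary outcomes list in section 1 also names hematocrit. That matches the Outcomes part of section 3 and the sample size, both of which use hemoglobin alone.

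**Conclusion.** The point holds as an optional improvement. The planned analysis is valid, and its power figure reproduces. Adjusting for day 1 hemoglobin would change power by about -1 to +2 points for an unselected correlation of up to 0.5. At 0.7 the gain is about 4 to 6 points under the main assumptions (SD 1.3, no lower bound). Under those assumptions the half-width would be between 0.83 and 0.76 g/dL, against 0.82 now. These figures depend on an assumed correlation and an assumed day 1 distribution, so confidence in the size of the gain is only moderate.

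The firmer argument is protection of the estimate. About one such trial in eight will show a baseline gap of at least 0.5 SD, and a pre-specified adjustment settles in advance how to handle it. The analysis would also report the baseline/6-week correlation and the residual SD in this restricted population. The larger trial could plan with both, and the present documents supply neither.

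**What to change.** If section 13 is being revised, add wording such as:

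> Primary analysis: linear model (ANCOVA) of 6-week hemoglobin on treatment arm, with postpartum day 1 hemoglobin as a continuous covariate. The adjusted mean difference is reported with its 95% CI; superiority is tested at two-sided 0.05. The Mann-Whitney test is a sensitivity analysis only.

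Keep N at 40, and add a sentence saying that the printed t-test calculation remains the basis for the sample size although the primary model is adjusted.

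The cost is this wording and one line of Stata. No new data are needed, because the day 1 value is already measured for eligibility. The model uses one degree of freedom (36 to 35) and gives up about 1 power point (0.820 to 0.809) if the correlation is near zero.

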**1. Introduction and Purpose:**

Postpartum anemia is a major global maternal health problem. In developing countries, postpartum anemia affects more than two thirds of women. In the United States, it affects 50% of mothers (1) and it has been linked to maternal morbidities such as impaired cognition, depression, and fatigue (2-5). Its negative impact on infant-mother bonding and neonatal care (6) has been reported. A major risk factor for postpartum anemia is iron deficient anemia in the antepartum period. The latter results from physiological changes in pregnancy; total blood volume increases by approximately 50% and red blood cell mass increases by 25% (7). The relative increase of blood volume compared to red blood cell mass causes a physiological anemia of pregnancy and therefore the hemoglobin and hematocrit threshold for diagnosing anemia in pregnancy are different than that of a non-pregnant adult. This increase in red blood cell mass, combined with the needs of the fetus, placenta, and normal anticipated blood loss from vaginal delivery represent a total additional need of 1,000 mg iron for a pregnancy, depleting maternal iron reserve (8-11). Oral iron supplementation is currently the standard of care for women with iron deficiency postpartum anemia (12,13). Up to 40% of patients do not tolerate oral iron (13), mainly due to gastrointestinal effects, leading to poor compliance and persistent anemia (14). Intravenous (IV) iron has advantages that bypass absorption challenges and may lead to faster recovery of iron stores and hemoglobin concentrations (11), with a proven safety record (16-17). Despite its advantages, IV iron is more costly and needs to be administered under supervision in a hospital or outpatient clinical setting. Two major reviews have evaluated the impact of IV iron in the postpartum period (18, 19). The first review did not find differences in maternal fatigue or maternal deaths, but did not report hematological effects such as postpartum hemoglobin. Four new randomized trials have been published comparing IV iron to oral iron therapy (20-23). An updated review of 15 randomized control trials (N=2182) concluded that hemoglobin concentrations at 6 weeks postpartum were almost 1 g/dL higher in women who received IV iron compared to oral iron (19). The safety profile of IV iron was also reassuring. Among the 15 trials included, only 2 were from the United States and neither one had 6 weeks postpartum hemoglobin as primary outcome. Hence, a large multicenter clinical trial is needed to adequately assess the impact of both modalities on hematological effects of postpartum anemia. Our aim is to perform a feasibility trial in order to guide a larger definite trial.

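### Does Section 13 overstate the trial's power by assuming a 1.2 g/dL difference when the cited review found just under 1 g/dL, and does the lack of a planned interval for the primary outcome matter?

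*Combined protocol and SAP*

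**What the plan says.** Section 13 (Biostatistics) takes from the literature, for the oral arm, a "mean 6 week postpartum hemoglobin of 11.2 g/dL with a standard deviation of 1.2". The IV-arm mean comes in a separate sentence, with no citation and no SD: "We anticipated that women that receive IV Iron will have a postpartum 6 weeks mean hemoglobin of 12.4 g/dL". The software output then lists "Effect size d = 0.9592329", two-sided alpha 0.05, target power 80%, 19 per group and actual power 0.8203999. A 5% loss to follow-up brings 38 up to 40.

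Section 1 (Introduction and Purpose) describes the same review that supplies the oral-arm figures. It pooled 15 trials and "concluded that hemoglobin concentrations at 6 weeks postpartum were almost 1 g/dL higher in women who received IV iron compared to oral iron". Section 5 (Criteria for Inclusion) restricts entry to hemoglobin below 9 g/dL. It argues that these women stand to gain most, and cites four studies from that review with baseline values of 7.4 to 8.1 g/dL, but gives no size of benefit. Section 2 (Concise Summary) says that 40 was chosen as a feasibility goal.

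On analysis, Section 13 says "We will be performing a superiority approach" and "P <0.05 will be considered significant". Continuous outcomes get a t test or rank-sum test, and "results will be given as mean, standard deviation or median range as appropriate". The only interval named is for binary outcomes: "For dichotomous endpoints, relative risk (RR) and 95% CI values will be calculated".

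**The concern.** The design borrows its oral-arm mean and SD from one review, yet assumes a larger treatment difference than the one it quotes from that review, and does not say why. If the true difference is nearer the quoted figure, power falls well below 80%, and Section 13 gives power at one difference only.

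The primary outcome is continuous, so as written it gets a P value and group summaries but no planned interval for the difference. A non-significant result in a trial of this size could then be misread as evidence of no benefit, although it would be compatible with a difference of 1 g/dL. That would matter because the trial is meant to inform the sample size of a larger one.

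**Working it through.** **Inputs.** From Section 13: means 11.2 and 12.4 g/dL, oral-arm SD 1.2, d = 0.9592329, two-sided alpha 0.05, 1:1 allocation, 19 per group, 5% loss. From Section 1: a difference of just under 1 g/dL, read here as 0.9 to 1.0. That reading is an assumption, because no exact figure is given.

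**Step 1: reproduce the plan's figure.**
- Noncentrality = d × √(n/2) = 0.9592329 × √(19/2) = 2.9566.
- Degrees of freedom = 36; critical t = 2.0281.
- Power from the noncentral t distribution = 0.8204, as printed. With 18 per group it is 0.7983, so 19 is the minimum.
- 38 / 0.95 = 40, as stated.

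**Step 2: the SD behind d.**
- Implied common SD = 1.2 / 0.9592329 = 1.251.
- With an oral SD of 1.2, the IV SD solves to √(2 × 1.251² − 1.2²) = 1.30. This is an inference; the document does not state it.
- With SD 1.2 in both arms, d = 1.0 and 17 per group would already give 80.7%. The printed d is therefore slightly conservative relative to the one SD written in the text.

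**Step 3: power at smaller differences, 19 per group.**

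| True difference (g/dL) | SD 1.251 | SD 1.2 |
|---|---|---|
| 1.2 | 82.0% | 85.1% |
| 1.0 | 66.9% | 70.5% |
| 0.9 | 57.8% | 61.4% |

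The difference detectable with 80% power is 1.17 g/dL (SD 1.251) or 1.12 g/dL (SD 1.2).

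**Step 4: what the interval would look like.**
- Half-width = t × SD × √(2/n) = 2.0281 × 1.251 × √(2/19) = 0.82 g/dL; with SD 1.2 it is 0.79.
- Example: an observed difference of 0.70 with SD 1.251 gives 0.70 ± 0.82, that is −0.12 to 1.52.
- Everything in this formula is either reported under the plan (means, SDs) or known (group sizes). The interval uses the same standard error as the t test.

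**Step 5: how often a missed effect stays compatible with 1 g/dL.** If the true difference is 1.0, a 95% interval misses 1.0 on the low side 2.5% of the time, and essentially all of those cases are non-significant. Among non-significant results, the share whose interval contains 1.0 is therefore about 1 − 0.025/0.331 = 0.92 (SD 1.251) or 1 − 0.025/0.295 = 0.92 (SD 1.2). This restates the power in Step 3; it is not a separate harm.

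**The case for a change.** The best case for a change runs as follows. Section 13 declares a superiority test at the 5% level, so the feasibility label does not remove the power question. Even at the top of the assumed range, exactly 1.0 g/dL, power with 19 per group is only 67% to 71%. The document offers no figure supporting 1.2 g/dL in women below 9 g/dL. A trial meant to guide a larger one needs an estimate with its precision more than a P value. If the rank-sum test is used and only median and range are given, a reader cannot recover an interval for the mean difference. Two sentences would settle all this at no cost to patients.

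Part of this stands. The power figures are right, Section 13 does not name an interval for the primary outcome, and in the rank-sum case the published summaries alone would not yield one.

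It does not carry a change, for three reasons. First, the benchmark is a pooled result over 15 trials, while this trial selects women with low hemoglobin, in whom a larger effect is plausible. Without the review's subgroup figures, nobody can show from the document that 1.2 g/dL is either right or optimistic. Second, listing power at more alternatives would alter neither N, the analysis nor any result. Third, the obvious wording brings faults of its own. Requiring a mean-difference interval whichever test is used would set a rank-sum P value beside a t-based interval, and the two can disagree about significance. Writing 1.25 into the plan as the SD would present a back-calculated value as a stated input.

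**Conclusion.** No change to the plan is needed. Section 13's sample size is correct for the alternative it states: 82.0% power with 38 completers, and 40 after 5% loss. No printed figure is wrong.

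The lower power of 58% to 71% rests on two assumptions: that the review's result means 0.9 to 1.0 g/dL, and that a pooled result applies to women below 9 g/dL. The range covers both the implied SD of 1.251 and the stated SD of 1.2. It is useful context for anyone reading a non-significant result, but it reveals no error, and the size was in any case fixed as a feasibility goal.

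The unnamed interval is a gap that a competent analyst fills without instruction. With the t test, it comes from the planned means and SDs. With the rank-sum test, the analyst holds the individual data and can give the matching shift estimate (Hodges-Lehmann) with its interval. With a half-width of about 0.8 g/dL, that interval will itself show how little a non-significant result excludes. The unstated IV-arm SD (1.30 reproduces the printed d) is a minor omission that makes the calculation slightly conservative.
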